2.5 Sample Size and Power

To estimate the required sample size for this study, we used ventilator-free days (VFD) data from the GRAIL Phase 2 trial and available literature on RSFDs, assuming similar variance. A clinically meaningful difference in RSFDs between treatment arms was assumed to be 2.74 days, with an empirically estimated standard deviation of 9.4 days. To detect this difference with 85% power using a two-sided test at a 5% significance level, a total sample size of 426 participants (213 per group) was required for the primary analysis.

To account for feasibility and potential dropout—including 1% lost to follow-up and 2% early discontinuation due to negative CMV ELISA results—the final sample size was increased to 500 participants. A pre-specified sample size re-estimation was conducted after 50% of participants had reached the primary endpoint; based on the observed data, the original sample size was retained.

Mortality was included as a secondary endpoint. Assuming a 20% mortality rate in the control arm, the final sample size of 500 provides 80% power to detect a hazard ratio of 0.52 between the Ganciclovir and placebo groups.

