In the GRAIL Phase 2 trial, VFDs difference was estimated to be 2.74 days. As shown in Table 6-2, to detect a similar difference (of 2.74 days) in RSFDs between the two arms with 85% statistical power, a sample size of 426 subjects ($213 \times 2 = 426$) total is required in this Phase 3 trial's primary analysis, and that is what we power for in this study. Findings from previous RCTs suggest that approximately 12% of subjects in this Phase 3 RCT will be CMV PCR positive at baseline when rapid lateral flow assay is used to assess serostatus. This 12% estimate is lower than the proportion reported in the GRAIL Phase 2 study due to the use of the rapid lateral flow assay, which we estimate will shorten the time to randomization from ICU admission by approximately 1 day and reduce the baseline PCR positivity rate. Furthermore, we anticipate that the percentage of subjects who are PCR positive at baseline will be lower among individuals on respiratory support (as defined in Section 4.1.1) compared with individuals on mechanical ventilation alone (as in the GRAIL Phase 2 trial) because we will be capturing some eligible participants earlier in the course of their respiratory failure when less time has elapsed to allow for CMV reactivation (both because we will allow enrollment of patients on NIV and HFNC oxygen and because time to obtain consent from participants able to consent for themselves may be shorter than consent through LARs. Since the population for primary analysis includes all patients without regard to PCR positivity at baseline, we inflate the sample size by a factor to

account for the power loss by including these cases in our primary analysis population. We also assume a dropout rate of 1% lost to follow-up for the primary endpoint, based on findings from other large ICU trials, and a dropout rate of 2% for early discontinuation following a negative CLIA CMV ELISA test among randomized participants who have received at least one dose of study drug. Accounting for both of these effects, the sample size for GRAIL Phase 3 trial was increased to 500 subjects in total.

6.1.2 Power Calculations for Secondary Endpoints.

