We will also compare the duration of mechanical ventilation and respiratory support by day 28 among survivors between the two intervention arms. If the rate of death by day 28 differs between the two groups, then the analysis in survivors may be biased. If there is evidence for a differential death rate, then a sensitivity analysis will be conducted to evaluate how the estimated mean difference changes with a range of assumptions about the degree of possible selection bias. The sensitivity analysis method of Shepherd will be used [91], which was designed to address “truncation by death”. A mediation analysis will also be conducted to test if CMV viremia lies in the causal pathway linking the treatment (Ganciclovir) effect with the outcome (RSFDs), that is,

if CMV viremia, which is assumed to be affected by the treatment, itself affects the outcome or not.

This analysis will be conducted in four steps:

1. A regression analysis with Treatment predicting RSFDs to test for path c alone,
2. A regression analysis with Treatment predicting CMV Viremia to test for path a,
3. A regression analysis with CMV Viremia predicting RSFDs to test the significance of path b,
4. A multiple regression analysis with Treatment and CMV Viremia predicting RSFDs.

The purpose of Steps 1-3 is to establish that zero-order relationships among the variables exist. If one or more of these relationships are non-significant, it can be concluded that mediation is not likely. If there are significant relationships in Steps 1 through 3, Step 4 is conducted. In the Step 4 model, some form of mediation is supported if the effect of CMV Viremia (path b) remains significant after controlling for Treatment. If Treatment is no longer significant when CMV Viremia is controlled, the finding supports full mediation. If effect of CMV Viremia is still significant, the finding supports partial mediation. Apart from this, static respiratory system compliance (Crs) will also be used in a separate mediation analysis to understand whether any effect of Ganciclovir is exerted via pulmonary mechanisms.

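### The step 4 mediation rule does not separate full from partial mediation: one result gets both labels, and another is called full mediation when none is supported

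*Combined protocol and SAP*

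**What the plan says.** Section 6.2.2 of the protocol sets out four regressions: treatment on RSFDs, treatment on CMV viremia, viremia on RSFDs, and finally "A multiple regression analysis with Treatment and CMV Viremia predicting RSFDs". The last is conditional on the others: "If there are significant relationships in Steps 1 through 3, Step 4 is conducted".

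Three sentences then interpret step 4:

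- **Any mediation:** "some form of mediation is supported if the effect of CMV Viremia (path b) remains significant after controlling for Treatment".
- **Full mediation:** "If Treatment is no longer significant when CMV Viremia is controlled, the finding supports full mediation".
- **Partial mediation:** "If effect of CMV Viremia is still significant, the finding supports partial mediation".

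The section adds a separate mediation analysis through static respiratory system compliance and gives no other rule for it. The separate SAP does not describe a mediation analysis in its general methods (section 5), primary, safety and secondary analyses (sections 8 to 10) or additional analyses (section 11). Its list of changes from the protocol (section 12) does not say that the analysis was altered or dropped.

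**The concern.** Full and partial mediation differ in whether treatment still has an effect once the mediator is in the model. The partial-mediation sentence does not look at treatment. It repeats the condition for any mediation, so it cannot tell the two labels apart. The full-mediation sentence looks only at treatment and does not require viremia to be significant, so read alone it can apply when viremia explains nothing.

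At stake is how the trial describes its mechanism: whether ganciclovir's effect on RSFDs is said to run wholly or only partly through CMV suppression. A prespecified rule should give one answer per result, without the analyst having to change the wording after seeing the data.

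**Working it through.** The documents give no figure for this rule, so there is nothing to reproduce. The check is to list the four possible step 4 results, given that steps 1 to 3 were significant, and apply the three sentences literally.

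| Viremia in step 4 | Treatment in step 4 | Any-mediation sentence met | Full sentence met | Partial sentence met | Literal conclusion |
|---|---|---|---|---|---|
| significant | significant | yes | no | yes | partial |
| significant | not significant | yes | yes | yes | full and partial |
| not significant | significant | no | no | no | none |
| not significant | not significant | no | yes | no | full, although no mediation is supported |

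Rows 2 and 4 are faulty. Row 2 is the result that the full-mediation sentence is meant to identify.

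Now make both labels conditional on viremia being significant, and separate them by treatment. The four rows become partial, full, none, none: one conclusion each. Changing only the subject of the partial sentence from viremia to treatment is not enough. Row 2 would then be full only, but row 4 would still read as full, and row 3 would newly read as partial although the any-mediation sentence is not met.

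**How often the faulty rows might arise (illustration only).** Inputs from the documents:

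- 500 participants ("the sample size for GRAIL Phase 3 trial was increased to 500 subjects in total", protocol 6.1.1), taken as 250 per arm.
- A difference of 2.74 days ("In the GRAIL Phase 2 trial, VFDs difference was estimated to be 2.74 days", protocol 6.1.1).
- An SD of 9.4 days ("with an empirically estimated standard deviation of 9.4 days", SAP 2.5).
- Two-sided 5% tests, and the control mean of 16.33 days from protocol Table 6-1.

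As a check that the design inputs were read correctly, the normal approximation gives n per arm = 2 × (1.960 + 1.036)² × (9.4/2.74)² ≈ 211.3, rounded up to 212. The protocol's t-based figure is 213.

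Assumptions not in the documents: viremia is yes/no, with 30% or 40% viremic on placebo and 10% on ganciclovir; 50%, 75% or 100% of the 2.74 days is mediated; nothing confounds viremia and RSFDs. The model was RSFD = 16.33 + b(M − p_C) + d·T + e. Here M is viremia, T is treatment, p_C and p_T are the viremia proportions on placebo and ganciclovir, b = −2.74 × share/(p_C − p_T), d = 2.74 × (1 − share), and e is normal with SD 9.4. For example, at 40% v 10% with all of the effect mediated, b = −2.74/0.30 = −9.13 days. There were 3,000 simulated trials per scenario.

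| Viremia, placebo v ganciclovir | Share mediated | Runs reaching step 4 | Row 2 (double label) | Row 1 | Row 3 | Row 4 |
|---|---|---|---|---|---|---|
| 40% v 10% | 100% | 2,593 | 2,505 (97%) | 88 | 0 | 0 |
| 40% v 10% | 75% | 2,625 | 2,289 (87%) | 336 | 0 | 0 |
| 40% v 10% | 50% | 2,662 | 1,685 (63%) | 960 | 12 | 5 |
| 30% v 10% | 100% | 2,393 | 2,321 (97%) | 72 | 0 | 0 |
| 30% v 10% | 75% | 2,553 | 2,196 (86%) | 357 | 0 | 0 |
| 30% v 10% | 50% | 2,658 | 1,578 (59%) | 1,080 | 0 | 0 |

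Under these assumptions, row 2 is the most common result once step 4 is reached. Row 4 is rare: at most 5 of 2,662, about 0.2%.

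**The case against.** The strongest reply is that this is a slip of the pen. Read in order (first any mediation, then full if treatment drops out, otherwise partial), the paragraph gives the intended labels, and most statisticians would read it that way. That is a fair account of the likely intent. But the text contains no otherwise, and no other passage in the two documents supplies one. The slip is easy to read past and equally easy to correct.

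The second reply is that it will seldom matter, and that stands. Step 4 needs a significant treatment effect on RSFDs, and SAP section 4 reports that enrollment was closed over safety and futility concerns. The documents give no results, but if step 1 is not significant the disputed sentence is never used. Mediation is also not named among the listed objectives or endpoints. SAP section 11 refers to a companion plan for exploratory and post hoc analyses, which is not among the documents reviewed and might restate the rule.

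A reader might also infer more than the text supports:

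- **That the faulty sentence decides whether the trial claims that ganciclovir acts through CMV suppression.** It does not. The any-mediation sentence decides that, and it is clear.
- **That every result called full is also called partial.** This holds only when viremia is significant. When neither term is significant, the full sentence is met and the partial one is not.

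**Conclusion.** The step 4 rule is wrong as written. Two of its four possible results are labelled wrongly: one is both full and partial, and the other is full with no mediation supported. This follows from the wording alone and rests on no numerical assumption. The 59% to 97% range for the doubly labelled result is conditional on reaching step 4 and depends on the assumed viremia rates and mediated shares. It should not be read as a forecast for this trial.

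The consequence is minor. It concerns the full-versus-partial label of a supporting mechanistic analysis, and only if steps 1 to 3 are all significant. The rule for whether any mediation is supported, the primary test, the sample size and the type I error are unaffected.

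**What to change.** Replace the full and partial sentences in protocol section 6.2.2 with a single rule: the labels apply only if CMV viremia remains significant in step 4; mediation is then called full if treatment is no longer significant, and partial if treatment is still significant. State that the same rule applies to the static compliance analysis, with compliance in place of viremia. If the companion plan repeats the rule, correct it there too. The cost is a sentence or two of text, with no change to data or trial conduct.

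Optionally, report the indirect and direct effects with bootstrap 95% confidence intervals, so that full mediation is not inferred from a non-significant treatment term alone. That is a small amount of extra analysis and is not needed to correct the error.

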8. PRIMARY ENDPOINT ANALYSES

The primary endpoint, respiratory-support-free days (RSFDs), is defined as 28 days minus the number of days a participant received respiratory support (including invasive mechanical ventilation, non-invasive ventilation with CPAP or bi-level CPAP and PEEP ≥ 5 cmH₂O, or high-flow nasal cannula oxygen with a flow rate ≥ 30 L/min) through Day 28 following randomization.

- Participants who do not survive through Day 28 will be assigned zero RSFDs.
- Participants who remain on respiratory support on Day 27 will be assigned zero RSFDs.
- Participants transferred to long-term acute care hospitals (LTACHs) will be assigned zero RSFDs.
- Participants who withdrew consent, refused further participation by themselves or a legally authorized representative (LAR), and for whom no further data were collected, or who withdrew due to study closure within the first 28 days will be considered missing for the RSFD endpoint.

RSFDs will be summarized descriptively using the mean, standard deviation, median, and range by treatment group. To formally test the primary hypothesis that the mean difference in RSFDs between treatment arms differs from zero, a two-sample parametric t-test will be used. This test is appropriate even if the normality assumption is mildly violated, given its robustness for moderate sample sizes ($n > 25$). As a confirmatory approach, a two-sample permutation t-test will also be performed. This nonparametric test does not require distributional assumptions and is valid under the weaker condition of exchangeability, which is satisfied in the randomized trial setting.

To further improve statistical efficiency and precision, the semiparametric efficient and robust method of Davidian et al. [7, 8] will be employed to estimate the mean difference between arms, along with its 95% confidence interval. This method adjusts for baseline characteristics predictive of the primary outcome and is more powerful than a conventional ANCOVA or t-test when baseline adjustment is warranted. If data on

the primary endpoint are missing for reasons other than death, the analysis will appropriately account for the missing data mechanism, as described in Protocol Section 6.4.1.

In addition to the ITT analysis, the primary endpoint will also be analyzed in a classical intent-to-treat (cITT) and two modified intent-to-treat (mITT) populations.

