First, biologically, we believe that CMV prophylaxis is likely to exert its greatest effect on pulmonary related morbidity. Second, VFDs (and more recently, RSFDs or organ support-free days) are frequently used as outcomes in high profile RCTs and influence clinical practice. A recent review of 128 RCTs assessing duration of mechanical ventilation in 10 high-profile general medical and critical care journals found that 43% reported VFDs and 12% used it as the primary outcome variable [81]. The NHLBI ARDS Network FACTT Trial showed that a conservative approach to fluid management increased VFDs by 2.5 with no statistically significant effect on mortality at 60 days [82]. Based primarily on this trial evidence, the Surviving Sepsis Guidelines endorsed this approach with a strong recommendation. Finally, VFDs are the outcome that was significantly improved in our phase 2 GRAIL RCT. Importantly, in recent trials enrolling NIV patients, there has been a change from VFDs to RSFDs and organ support free days in a 28 day window [83–85]. For example, the REMAP-CAP platform trials for COVID and community acquired pneumonia have adopted RSFDs and have determined that 1.5 RSFDs are the minimal clinically important difference [84].

There are several possible limitations to using RSFDs at 28 days as our primary endpoint. As with all composites, patients and clinicians may not value these outcomes in the way they are weighted in the composite. RSFDs will not capture outcomes that go in different directions (e.g., treatments that increase mortality but also reduce duration of respiratory support in survivors). RSFDs can be difficult to interpret as they do not simply reflect either a change in mortality or a difference in duration of respiratory support. Generally, VFDs have a bi-modal distribution and must be analyzed appropriately [81]; we anticipate that the distribution of RSFDs will also have a bi-modal distribution.

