6 STATISTICAL CONSIDERATIONS

6.1 Power Calculations for Primary and Secondary Hypotheses

6.1.1 Primary Endpoint

The primary endpoint RSFD is defined as follows.

Consistent with use of free-days in other studies, RSFDs will use a “last off” approach. This is the approach that has been used in PETAL Network studies (e.g., NCT02509078), is preferred by FDA as a more durable/sustained recovery landmark, and recommended by our External Advisory Board.

“Last off” means that RSFDs will be counted when a participant gets off and stays off of respiratory support (as defined in Section 4.1.1) to day 28. Days off of respiratory support will be counted back from day 28 to the last day when respiratory support was received. If a participant is still receiving respiratory support on day 28, no RSFDs will be counted, even if they were not receiving support for some number of days before day 28. Following are 3 examples of this calculation:

1. Participant receives respiratory support from days 1-10 and then receives no further respiratory support through day 28. RSFDs=18.
2. Participant receives respiratory support from days 1-10, then again from 16-20, then again from 24-26. No respiratory support is received on days 27 or 28. RSFDs=2.
3. Participant receives respiratory support from days 1-10, then again from 26-28. RSFDs=0.

Participants who do not survive to day 28 are assigned zero respiratory-support-free days [23, 88]. The 28-day landmark is chosen, because

1. Interventional trials in acute respiratory failure typically involve a 28-day treatment or follow-up period after the patient enrolls in the trial; and
2. Most patients with acute respiratory failure have either died or been successfully weaned from respiratory support by day 28 [23, 88].

To estimate the required sample size for the trial with adequate statistical power for the primary endpoint, we used the data of VFDs in the ganciclovir and placebo arms of the GRAIL Phase 2 trial and available RSFD data in the literature [83-85]. The summary statistics of VFDs in the sepsis cohort of GRAIL Phase 2 trial are shown in the table below. Since standard deviation data for RSFD is sparse, we assume that standard deviation for RSFDs is similar to that of VFDs in our sample size calculations as informed by Table 6-1.

Table 6-1. Summary statistics of VFDs in the Sepsis Cohort of GRAIL Phase 2 Trial

	n	Min	Q1	Med	Mean	Q3	Max	StD
Control	66	0	9.0	20	16.33	24	27	9.62
Treatment	71	0	16.5	23	19.07	25	27	9.25

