Alternative approaches to Analyze RSFDs. Our secondary analysis plan also includes a pipeline for exploring alternative approaches to analyze RSFDs. Given that RSFDs are increasingly being used as an outcome in high profile RCTs (as mentioned in Section 4.5.1, RSFDs or organ support-free days have been used as the primary endpoint in several recent high-profile RCTs [83-85]), these proposed statistical considerations can serve as a reference point for RSFD analyses in future clinical trials. Thus, we believe this to be one of the statistical innovations proposed by the Data Coordinating Center (DCC) for this Phase 3 trial.

One important limitation to using RSFDs as an endpoint arises, as previously stated, due to its composite nature. RSFD assigns points based on counting back from day 28 to the last day when respiratory support was received (see Section 6.1.1). The outcome also considers mortality and assigns an overall score of zero points to those who die within those first 28 days. Thus, the composite nature of this endpoint leads to it being a zero-inflated binomial random variable, which has a mixture distribution of a degenerate 0 and a binomial distribution. That is, we can write

$$RSFDs \sim \pi \times 0 + (1 - \pi) \times Bi(28, p)$$

where π is the probability that a death occurs, and $Bi(28, p)$ is a binomial distribution such that p is the probability of a subject experiencing a RSFD while being alive through the specified window, that is desired to be modeled. The zero inflated binomial response is a special instance of over-dispersed responses, and there is considerable literature on the numerous challenges and

statistical issues when modeling such data [92, 93]. Thus, modeling of RSFDs can be handled through a number of approaches:

1. Account for over-dispersion through the zero-inflated binomial model: The zero-inflated binomial model is obtained by mixing a degenerate distribution at zero with a standard binomial distribution [94, 95], and has been subsequently used in epidemiology and health economics to model binomial counts with excessive zeros. The zero-inflated binomial model will be used as an alternative approach to model RSFDs in this analysis.

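### The exploratory zero-inflated RSFD model labels its zero component as death, but survivors still on support also score zero, so π is the probability of a zero score and not mortality

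*Combined protocol and SAP*

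**What the plan says.** Under the alternative approaches in protocol section 6.2.2, RSFDs are written as a mixture: zero with weight π, and Bi(28, p) with weight 1 − π. The text states that π "is the probability that a death occurs" and that p "is the probability of a subject experiencing a RSFD while being alive through the specified window". The model is listed first among several ways of handling over-dispersion.

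The endpoint itself gives zeros by more than one route:

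- Death, protocol 6.1.1: "Participants who do not survive to day 28 are assigned zero respiratory-support-free days".
- Alive but on support, protocol 6.1.1: "If a participant is still receiving respiratory support on day 28, no RSFDs will be counted". The third worked example there is a zero with no death in it: "Participant receives respiratory support from days 1-10, then again from 26-28. RSFDs=0".
- On support on Day 27, SAP section 8: "Participants who remain on respiratory support on Day 27 will be assigned zero RSFDs".
- LTACH transfer, SAP section 8 only: "Participants transferred to long-term acute care hospitals (LTACHs) will be assigned zero RSFDs".

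Protocol 6.1.1 also notes that most, not all, patients have died or been weaned by day 28, so some living zeros are to be expected.

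**The concern.** The definition of π and the endpoint rules cannot both hold. If the only zeros were deaths, π would be mortality. Because some survivors also score zero, the zero component collects two kinds of participant, and its label names only one of them.

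What is at stake is how a treatment effect on π would be read. Protocol 4.5.1 concedes of the composite that "RSFDs will not capture outcomes that go in different directions", giving as its example a treatment that raises mortality but shortens support in survivors. A parameter labelled death but fed by both deaths and prolonged support has the same limitation under a more specific name. Fewer survivors left on support would lower π with no change in deaths. A rise in deaths could be matched by fewer such survivors and leave π unchanged.

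**Working it through.** **The plan's nearest figure.** The documents give no figure for this model. The closest is the detectable mortality hazard ratio of 0.52 (protocol 6.1.2, Table 6-3: 500 participants, 20% control mortality, 80% power, two-sided 5%). The treated risk is 1 − 0.80^0.52 = 0.110. A two-proportion comparison of 0.20 with 0.110 at 250 per arm has power 0.800, so the figure reproduces.

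**Inputs.** Death risk d = 20% (protocol 6.1.2) and 250 per arm (protocol section 1). The share s of day-28 survivors who score zero is not in the documents; I assume 0, 5, 10 and 15%.

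**Step 1: can the binomial part absorb survivor zeros?** P(0) under Bi(28, p) is (1 − p)^28.

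- Table 6-1 gives a control mean of 16.33 VFDs. 16.33/28 = 0.58 is a floor for p on that scale, because the mean includes the zeros. (1 − 0.583)^28 ≈ 2 × 10⁻¹¹.
- At p = 0.71, about 10⁻¹⁵. At p = 0.5, about 4 × 10⁻⁹.
- Even at p = 0.2, only 0.2%.

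So almost every survivor zero goes to π.

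**Step 2: what π estimates.** P(RSFD = 0) = d + (1 − d)s. With d = 0.20:

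- s = 0: 0.20
- s = 5%: 0.20 + 0.80 × 0.05 = 0.24
- s = 10%: 0.28
- s = 15%: 0.32

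Maximum-likelihood fits to 200,000 simulated participants per arm agreed with these values to within 0.002. Positive survivor scores were drawn from a dispersed distribution with mean near 70% of 28 days.

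**Step 3: dilution.** Take deaths of 20% versus 30% with the same s in both arms. The death odds ratio is (0.30/0.70)/(0.20/0.80) = 1.71. Power is for comparing the two zero proportions, Φ{(|p₁ − p₂| − 1.96·SE₀)/SE₁}, with SE₀ pooled and SE₁ unpooled.

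| s | π, 20% deaths | π, 30% deaths | OR for π | Power |
|---|---|---|---|---|
| 0 | 0.200 | 0.300 | 1.71 | 0.73 |
| 5% | 0.240 | 0.335 | 1.60 | 0.65 |
| 10% | 0.280 | 0.370 | 1.51 | 0.58 |
| 15% | 0.320 | 0.405 | 1.45 | 0.51 |

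**Step 4: cancellation.** Let the control arm have d = 20% and s = 15%, so π = 0.32.

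- Treated d = 26%, s = 8.1%: 0.26 + 0.74 × 0.081 = 0.32. The OR for π is 1.00; the death OR is 1.41.
- Treated d = 30%, s = 2.9%: 0.30 + 0.70 × 0.029 = 0.32. The OR for π is 1.00; the death OR is 1.71.

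**Step 5: the direct death comparison.** Schoenfeld power for the planned Cox analysis does not involve s.

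- 20% versus 26%: 250 × 0.46 = 115 deaths, HR = ln 0.74/ln 0.80 = 1.35, power about 0.36.
- 20% versus 30%: 125 deaths, HR = 1.60, power about 0.75.

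**The case against.** The strongest reply is that nothing in the trial turns on π. The model is one of several exploratory alternatives and is headed as a treatment of over-dispersion. Section 6.2.2 names p, not π, as the quantity to be modelled. Splitting the composite is a different item in the same list, which fits a Cox model to time to death. The SAP does not list the zero-inflated model at all, although its section on changes from the protocol does not withdraw it. The companion plan for exploratory analyses is not among the documents. The LTACH rule is in the SAP only, so that part of the conflict runs across two documents. All of this stands and limits the weight of the point. It does not remove the conflict, which exists within the protocol between 6.1.1 and 6.2.2.

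A reader might go further and infer that the plan could hide excess deaths. The documents do not support that. Besides the Cox model in 6.2.2, mortality is a secondary endpoint with Kaplan–Meier, log-rank and Cox analyses (SAP sections 9 and 10). Deaths also have their own O'Brien–Fleming interim boundary (protocol 6.5.1.1). None of these depends on survivors who score zero. Nor does any section say that an effect on π will be reported as a mortality effect. SAP section 4 records closure of enrolment over safety and futility concerns, but nothing links that decision to this model.

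It is also fair to object that s is assumed and that the cancelling examples were chosen to cancel exactly. They show what can happen, not what did.

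**Conclusion.** The definition of π is wrong as written, at low severity. Under the protocol's own endpoint rule, π estimates the probability of zero RSFDs from any cause. At 20% mortality it would exceed the death risk by 4 to 12 percentage points if 5 to 15% of survivors score zero. With equal shares in both arms, a death odds ratio of 1.71 would appear as 1.60 to 1.45. With opposing effects it could appear as 1.00.

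That π is not mortality follows from the endpoint rules and from the negligible binomial mass at zero. The sizes rest on the assumed range for s. The consequence is confined to how π is read: a π effect could seem to disagree with the Cox result for purely definitional reasons. The primary t-test, the mortality analyses and the interim safety boundary are untouched.

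**What to change.** Redefine π as the probability of zero RSFDs from any cause: death, support at the end of follow-up or, under the SAP, LTACH transfer. State that no mortality conclusion will be drawn from it. This costs one sentence.

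If a death component is wanted within this model, use the death indicator, which is observed and need not be inferred from zeros:

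1. A logistic model for death by Day 28.
2. A beta-binomial model, or a binomial model with robust variance, for RSFDs in survivors with their zeros kept.

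Label the second part as conditional on survival, and read it alongside the truncation-by-death sensitivity analysis that protocol 6.2.2 already plans for survivor comparisons if death rates differ. The companion model for time off support in 6.2.2 does not fill this role, because it is fitted regardless of mortality status. The cost is a few lines of code on the same data; the downside is that the survivor part is not a randomised comparison.

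The new definition should use one rule for the end of follow-up. Support that ends on day 27 scores 1 by the protocol's count-back and 0 under SAP section 8, so the two sections need to be reconciled.
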